### 9.3.2. Post-Study adverse events and serious adverse events

A post-study AE/SAE is defined as any event that occurs outside of the AE/SAE reporting period defined in [Table 19](#).

Investigators are not obligated to actively seek AEs or SAEs in former study participants. However, if the investigator learns of any SAE at any time after a subject has been discharged from the study, and he/she considers the event reasonably related to the study vaccine the investigator will promptly notify the Study Contact for Reporting SAEs.

### 9.3.3. Evaluation of adverse events and serious adverse events

#### 9.3.3.1. Active questioning to detect adverse events and serious adverse events

As a consistent method of collecting AEs, the subject's parent(s)/LAR(s) should be asked a non-leading question such as:

*'Has your child acted differently or felt different in any way since receiving the vaccine or since the last visit?'*

When an AE/SAE occurs, it is the responsibility of the investigator to review all documentation (e.g., hospital progress notes, laboratory and diagnostics reports) relative to the event. The investigator will then record all relevant information regarding an AE/SAE in the eCRF. The investigator is not allowed to send photocopies of the subject's medical records to GSK Biologicals instead of appropriately completing the eCRF. However, there may be instances when copies of medical records for certain cases are requested by GSK Biologicals. In this instance, all subject identifiers will be blinded on the copies of the medical records prior to submission to GSK Biologicals. ***For countries where it is not acceptable to provide copies of medical records to the sponsor, the required information will be transcribed by the investigator and provided to GSK respecting the subject's anonymization (Amended 1 August 2019).***

The investigator will attempt to establish a diagnosis pertaining to the event based on signs, symptoms, and/or other clinical information. In such cases, the diagnosis should be documented as the AE/SAE and not the individual signs/symptoms.

**9.3.3.2. Assessment of adverse events****9.3.3.2.1. Assessment of intensity**

The intensity of the following solicited AEs will be assessed as described:

**Table 20 Intensity scales for solicited symptoms in infants**

Infant		
Adverse Event	Intensity grade	Parameter
Pain at injection site	0	None
	1	Mild: Minor reaction to touch
	2	Moderate: Cries/protests on touch
	3	Severe: Cries when limb is moved/spontaneously painful
Redness at injection site		Record greatest surface diameter in mm
Swelling at injection site		Record greatest surface diameter in mm
Fever*		Record temperature in °C/°F
Irritability/Fussiness	0	Behaviour as usual
	1	Mild: Crying more than usual/no effect on normal activity
	2	Moderate: Crying more than usual/interferes with normal activity
	3	Severe: Crying that cannot be comforted/prevents normal activity
Drowsiness	0	Behaviour as usual
	1	Mild: Drowsiness easily tolerated
	2	Moderate: Drowsiness that interferes with normal activity
	3	Severe: Drowsiness that prevents normal activity
Loss of appetite	0	Appetite as usual
	1	Mild: Eating less than usual/no effect on normal activity
	2	Moderate: Eating less than usual/interferes with normal activity
	3	Severe: Not eating at all

\* Fever is defined as temperature  $\geq 38.0^{\circ}\text{C} / 100.4^{\circ}\text{F}$  by any route. The preferred location for measuring temperature in this study will be the axilla for subjects  $\geq 1$  and  $< 5$  years of age and the rectum for subjects  $< 12$  months of age.

The maximum intensity of local injection site redness and swelling will be scored at GSK Biologicals as follows:

0	:	None
1	:	< 5 mm
2	:	5 to 20 mm
3	:	> 20 mm

The maximum intensity of fever will be scored at GSK Biologicals as follows:

0	:	< $38.0^{\circ}\text{C}/100.4^{\circ}\text{F}$
1	:	$\geq 38.0^{\circ}\text{C}/100.4^{\circ}\text{F}$ to $\leq 39.0^{\circ}\text{C}/102.2^{\circ}\text{F}$
2	:	$> 39.0^{\circ}\text{C}/102.2^{\circ}\text{F}$ to $\leq 40.0^{\circ}\text{C}/104.0^{\circ}\text{F}$
3	:	$> 40.0^{\circ}\text{C}/104.0^{\circ}\text{F}$

The investigator will assess the maximum intensity that occurred over the duration of the event for all unsolicited AEs (including SAEs) recorded during the study. The assessment will be based on the investigator's clinical judgement.

The intensity should be assigned to one of the following categories:

- 1 (mild) = An AE which is easily tolerated by the subject, causing minimal discomfort and not interfering with everyday activities.
- 2 (moderate) = An AE which is sufficiently discomforting to interfere with normal everyday activities.
- 3 (severe) = An AE which prevents normal, everyday activities. Such an AE would, for example, prevent attendance at school/kindergarten/a day-care centre and would cause the parent(s)/LAR(s) to seek medical advice.

An AE that is assessed as Grade 3 (severe) should not be confused with a SAE. Grade 3 is a category used for rating the intensity of an event; and both AEs and SAEs can be assessed as Grade 3. An event is defined as 'serious' when it meets one of the pre-defined outcomes as described in Section 9.1.2.

#### ***9.3.3.2.2. Assessment of causality***

The investigator is obligated to assess the relationship between study vaccines and the occurrence of each AE/SAE using clinical judgement.

Alternative plausible causes, such as natural history of the underlying diseases, concomitant therapy, other risk factors, and the temporal relationship of the event to the study vaccines will be considered and investigated. The investigator will also consult the IB to determine his/her assessment.

There may be situations when a SAE has occurred and the investigator has minimal information to include in the initial report to GSK Biologicals. However, it is very important that the investigator always makes an assessment of causality for every event prior to submission of the Expedited Adverse Events Report to GSK Biologicals. The investigator may change his/her opinion of causality in light of follow-up information and update the SAE information accordingly. The causality assessment is one of the criteria used when determining regulatory reporting requirements.

All solicited local (injection site) reactions will be considered causally related to vaccination. Causality of all other AEs should be assessed by the investigator using the following question:

*Is there a reasonable possibility that the AE may have been caused by the study vaccine?*

YES : There is a reasonable possibility that the study vaccine contributed to the AE.

NO : There is no reasonable possibility that the AE is causally related to the administration of the study vaccine. There are other, more likely causes and administration of the study vaccine is not suspected to have contributed to the AE.

If an event meets the criteria to be determined as 'serious' (see Section 9.1.2), additional examinations/tests will be performed by the investigator in order to determine ALL possible contributing factors for each SAE.

Possible contributing factors include:

- Medical history.
- Other medication.
- Protocol required procedure.
- Other procedure not required by the protocol.
- Lack of efficacy of the vaccine, if applicable.
- Erroneous administration.
- Other cause (specify).

#### **9.3.3.3. Assessment of outcomes**

The investigator will assess the outcome of all unsolicited AEs (including SAEs) recorded during the study as:

- Recovered/resolved.
- Recovering/resolving.
- Not recovered/not resolved.
- Recovered with sequelae/resolved with sequelae.
- Fatal (SAEs only).

#### **9.3.3.4. Medically attended visits**

For each solicited and unsolicited symptom the subject experiences, the subject's parent(s)/LAR(s) will be asked if the subject received medical attention defined as hospitalization, or an otherwise unscheduled visit to or from medical personnel for any reason, including emergency room visits. This information will be recorded in the eCRF.

## 9.4. Reporting of serious adverse events and adverse events of special interest

### 9.4.1. Prompt reporting of serious adverse events and adverse events of special interest to GSK Biologicals

SAEs that occur in the time period defined in Section 9.3 will be reported promptly to GSK within the timeframes described in Table 21, once the investigator determines that the event meets the protocol definition of a SAE.

AEs of special interest (RSV-LRTI and spontaneous or excessive bleeding) that occur in the time period defined in Section 9.3 will be reported promptly to GSK within the timeframes described in Table 21.

**Table 21 Timeframes for submitting serious adverse event and adverse events of special interest reports to GSK Biologicals**

Type of Event	Initial Reports		Follow-up of Relevant Information on a Previous Report	
	Timeframe	Documents	Timeframe	Documents
SAEs	24 hours*†	electronic Expedited Adverse Events Report	24 hours*	electronic Expedited Adverse Events Report
AEs of special interest (RSV-LRTI)	24 hours*†	electronic Expedited Adverse Events Report	24 hours*‡	electronic Expedited Adverse Events Report
AE of special interest (spontaneous or excessive bleeding)	24 hours*†	electronic Expedited Adverse Events Report	24 hours*	electronic Expedited Adverse Events Report

\* Timeframe allowed after receipt or awareness of the information.

† The investigator will be required to confirm review of the SAE/ AE of special interest causality by ticking the 'reviewed' box in the electronic Expedited Adverse Events Report within 72 hours of submission of the SAE/ AE of special interest.

‡ In the timeframe of awareness for the local RSV test result.

**9.4.3. Completion and transmission of SAE reports to GSK Biologicals**

Once an investigator becomes aware that a SAE has occurred in a study subject, the investigator (or designate) must complete the information in the electronic Expedited Adverse Events Report **WITHIN 24 HOURS**. The report will always be completed as thoroughly as possible with all available details of the event. Even if the investigator does not have all information regarding a SAE, the report should still be completed within 24 hours. Once additional relevant information is received, the report should be updated **WITHIN 24 HOURS**.

The investigator will always provide an assessment of causality at the time of the initial report. The investigator will be required to confirm the review of the SAE causality by ticking the 'reviewed' box in the electronic Expedited Adverse Events Report within 72 hours of submission of the SAE.

**9.4.3.1. Back-up system in case the electronic reporting system does not work**

If the electronic reporting system does not work, the investigator (or designate) must complete, then date and sign a paper Expedited Adverse Events Report and fax it to the Study Contact for Reporting SAEs (refer to the [Sponsor Information](#)) or to GSK Biologicals Clinical Safety and Pharmacovigilance department within 24 hours.

This back-up system should only be used if the electronic reporting system is not working and NOT if the system is slow. As soon as the electronic reporting system is working again, the investigator (or designate) must complete the electronic Expedited Adverse Events Report within 24 hours. The final valid information for regulatory reporting will be the information reported through the electronic SAE reporting system.

**9.4.4. Reporting of adverse events of special interest to GSK Biologicals****9.4.4.1. RSV-LRTI**

**Note that ALL LRTI meeting the criteria of an SAE should be reported as SAEs with the timing of SAE reports.**

In addition, once an investigator becomes aware that an episode of LRTI not meeting the criteria of an SAE, but which has been confirmed on local testing to be due to RSV has occurred in a study subject, the investigator (or designate) must complete the information in the electronic Expedited Adverse Events Report **WITHIN 24 HOURS**. The report will always be completed as thoroughly as possible with all available details of the event. Later additional relevant information is received, the report should be updated **WITHIN 24 HOURS**.

The investigator will always provide an assessment of causality at the time of the initial report. The investigator will be required to confirm the review of causality by ticking the 'reviewed' box in the electronic Expedited Adverse Events Report within 72 hours of submission of the AE of special interest.

Refer to Section 9.4.3.1 for back-up system in case the electronic reporting system does not work.

#### **9.4.4.2. Spontaneous or excessive bleeding**

Once an investigator becomes aware that an episode of spontaneous or excessive bleeding has occurred in a study subject, the investigator (or designate) must complete the information in the electronic Expedited Adverse Events Report **WITHIN 24 HOURS**. The report will always be completed as thoroughly as possible with all available details of the event. Even if the investigator does not have all information regarding the event of spontaneous or excessive bleeding the report should still be completed within 24 hours. Once additional relevant information is received, the report should be updated **WITHIN 24 HOURS**.

The investigator will always provide an assessment of causality at the time of the initial report. The investigator will be required to confirm the review of causality by ticking the ‘reviewed’ box in the electronic Expedited Adverse Events Report within 72 hours of submission of the AE of special interest.

Refer to Section 9.4.3.1 for back-up system in case the electronic reporting system does not work.

#### **9.4.5. Updating of serious adverse event and adverse event of special interest information after removal of write access to the subject's eCRF**

When additional SAE or AE of special interest information is received after removal of the write access to the subject's eCRF, new or updated information should be recorded on the appropriate paper report, with all changes signed and dated by the investigator. The updated report should be faxed to the Study Contact for Reporting SAEs (refer to the [Sponsor Information](#)) or to GSK Biologicals Clinical Safety and Pharmacovigilance department within the designated reporting time frames specified in [Table 21](#).

#### **9.4.6. Regulatory reporting requirements for serious adverse events**

The investigator will promptly report all SAEs to GSK in accordance with the procedures detailed in Section 9.4.1. GSK Biologicals has a legal responsibility to promptly notify, as appropriate, both the local regulatory authority and other regulatory agencies about the safety of a product under clinical investigation. Prompt notification of SAEs by the investigator to the Study Contact for Reporting SAEs is essential so that legal obligations and ethical responsibilities towards the safety of other subjects are met.

Investigator safety reports are prepared according to the current GSK policy and are forwarded to investigators as necessary. An investigator safety report is prepared for a SAE(s) that is both attributable to the study vaccines and unexpected. The purpose of the report is to fulfil specific regulatory and GCP requirements, regarding the product under investigation.

## **9.5. Follow-up of adverse events, serious adverse events and adverse events of special interest**

### **9.5.1. Follow-up during the study**

After the initial AE, AE of special interest or SAE report, the investigator is required to proactively follow each subject and provide additional relevant information on the subject's condition to GSK Biologicals (within 24 hours for AEs of special interest and SAEs; refer to [Table 21](#)).

All AEs of special interest (RSV-LRTI) and SAEs documented at a previous visit/contact and designated as not recovered/not resolved or recovering/resolving will be reviewed at subsequent visits/contacts until the last visit of the subject.

All AE of special interest (spontaneous or excessive bleeding) documented at a previous visit/contact and designated as not recovered/not resolved or recovering/resolving will be reviewed at subsequent visits/contacts until 30 days after the last vaccination.

All AEs documented at a previous visit/contact and designated as not recovered/not resolved or recovering/resolving will be reviewed at subsequent visits/contacts until 30 days after the last vaccination.

#### **9.5.1.1. Follow-up after the subject is discharged from the study**

The investigator will follow subjects:

- with SAEs, with AEs of special interest or subjects withdrawn from the study as a result of an AE, until the event has resolved, subsided, stabilised, disappeared, or until the event is otherwise explained, or the subject is lost to follow-up.

If the investigator receives additional relevant information on a previously reported SAE, he/she will provide this information to GSK Biologicals using a paper/ electronic Expedited Adverse Events Report and/or pregnancy report as applicable.

GSK Biologicals may request that the investigator performs or arranges the conduct of additional clinical examinations/tests and/or evaluations to elucidate as fully as possible the nature and/or causality of the AE or SAE. The investigator is obliged to assist. If a subject dies during participation in the study or during a recognised follow-up period, GSK Biologicals will be provided with any available post-mortem findings, including histopathology.

## **9.6. Treatment of adverse events**

Treatment of any AE is at the sole discretion of the investigator and according to current good medical practice. Any medication administered for the treatment of a SAE and AE of special interest should be recorded in Expedited Adverse Event Report of the subject's eCRF (refer to Section [7.6](#)).

## 9.7. Unblinding

GSK Biologicals' policy (which incorporates ICH E2A guidance, EU Clinical Trial Directive and US Federal Regulations) is to unblind the report of any SAE which is unexpected and attributable/suspected to be attributable to the study vaccines, prior to regulatory reporting. The GSK Biologicals' Central Safety Physician is responsible for unblinding the treatment assignment in accordance with the specified timeframes for expedited reporting of SAEs (refer to Section 9.4.1).

## 9.8. Emergency unblinding

Unblinding of a subject's individual treatment code should occur only in the case of a medical emergency, or in the event of a serious medical condition, when knowledge of the treatment is essential for the clinical management or welfare of the subject, as judged by the investigator.

The emergency unblinding process consists of the automated system SBIR that allows the investigator to have unrestricted, immediate and direct access to the subject's individual study treatment.

The investigator has the option of contacting a GSK Biologicals' On-call Central Safety Physician (or Backup) if he/she needs medical advice or needs the support of GSK to perform the unblinding (i.e., he/she cannot access SBIR).

Any emergency unblinding must be fully documented by using the Emergency Unblinding Documentation Form, which must be appropriately completed by the investigator and sent within 24 hours to GSK Biologicals.

GSK Biologicals' Contact information for Emergency Unblinding	
24/24 hour and 7/7 day availability	
GSK Biologicals' Central Safety Physician:	
Worldwide except US/Canada: PPD [REDACTED] (GSK Biologicals Central Safety Physician on-call)	
For US/Canada only: PPD [REDACTED] (GSK Biologicals Central Safety Physician on-call)	
GSK Biologicals' Central Safety Physician Back-up:	
Worldwide except US/Canada: PPD [REDACTED]	
US/Canada only: PPD [REDACTED]	
Emergency Unblinding Documentation Form transmission:	
Worldwide except US & Canada: Fax: PPD [REDACTED] or PPD [REDACTED]	
US/Canada only: Fax: PPD [REDACTED]	

## 9.9. Subject card

Study subjects' parent(s)/LAR(s) must be provided with the address and telephone number of the main contact for information about the clinical study.

The investigator (or designate) must therefore provide a "subject card" to each subject's parent(s)/LAR(s). In an emergency situation this card serves to inform the responsible attending physician that the subject is in a clinical study and that relevant information may be obtained by contacting the investigator.

Subjects' parent(s)/LAR(s) must be instructed to keep subject cards in their possession at all times during the study duration.

## 9.10. Holding rules and safety monitoring

The investigational ChAd155-RSV vaccine has never been administered to RSV-potentially naïve infants. Safety precautions such as limited vaccination, safety evaluations by an iSRC and an IDMC, and study holding rules have therefore been defined.

### 9.10.1. Limited vaccination

In the same investigational center, all the infants should be vaccinated sequentially and at least 60 minutes apart to allow monitoring of any acute events (e.g., hypersensitivity reaction). All infants should be closely observed (visual follow-up as well as measurement of vital signs) for at least 60 minutes after vaccination. Vital signs are body temperature, HR and RR. Vital signs are preferably measured when the infant is calm.

### 9.10.2. Internal safety review committee (iSRC) oversight

This study will be overseen by an iSRC operating under a charter. An iSRC was already involved in study RSV PED-002 (204838). Core members of the iSRC will include a GSK Biologicals' safety physician, a CRDL, and a biostatistician who are not otherwise involved in the conduct of the project. The iSRC safety reviews will be conducted using unblinded data. The iSRC has access to the subject randomization and reviews unblinded data.

The iSRC will review all accumulating safety and reactogenicity data four weeks after the start of vaccination and then every 4 weeks until all dosing with ChAd155-RSV vaccine is complete on the study. The iSRC members will determine if a safety signal should be escalated to the VSMB. The iSRC members will determine whether any of the predefined holding rules are met (refer to Section 9.10.4) or if there is any other safety signal. In this case, vaccination in the study will be immediately put on hold (refer to Section 9.10.5).

The iSRC will receive the following safety data within 48 hours upon GSK becoming aware of:

- Fatal SAEs.
- Life-threatening SAEs.
- Related SAEs.
- SAEs occurring within 30 days of vaccination.
- LRTI associated with RSV infection (AE of special interest) occurring from Day 1 to the end of the second RSV transmission season.
- Spontaneous or excessive bleeding (AE of special interest) occurring within 30 days after each vaccination.

In addition, the iSRC will receive:

- Unblinded summary reports of accumulated solicited AEs and unsolicited AEs.
- New information that may adversely affect the safety of the subjects or the conduct of the study.
- All subsequent protocol amendments or administrative changes (for information).

### **9.10.3. Independent Data Monitoring Committee (IDMC) oversight**

This study will be overseen by an IDMC operating under a charter. The IDMC involved in the present study was already involved in study RSV PED-002 (204838). Overall, the role of the IDMC includes the review and protection of data integrity and rights and safety of study participants throughout the study period. It will provide initial, regular, and closing advice to GSK Biologicals on medical, ethical, scientific and safety-related issues. Its advice will be based on the interpretation of study data with reference to the study protocol.

The IDMC will review the protocol and statistical analysis plan. Meetings will be documented and minutes of open sessions of the IDMC meetings made available to the sponsor. The IDMC may, if deemed necessary, convene a meeting with, or request further information from the principal investigators and GSK Biologicals' designated project representatives at any stage of the study.

The IDMC may recommend to the sponsor to suspend the enrolment to the study and/or vaccination based on their review of safety data arising in this study (refer to Section [9.10.4](#)).

The IDMC safety reviews will be conducted using unblinded data. The IDMC will review all available safety data while taking into account any other findings that could have an impact on the safety of the subjects.

The IDMC members will determine whether any of the predefined study holding rules are met (refer to Section [9.10.4](#)) or if there is any other safety signal. If this is the case, vaccination in the study will be immediately put on hold. If no safety signal is observed,

the favorable outcome of the safety evaluation authorizing the investigator to proceed with vaccination of infants as outlined in [Figure 1](#) will be also documented and provided in writing.

- The IDMC will receive the following safety data within 48 hours upon GSK becoming aware of:
  - Fatal SAEs occurring from Day 1 to the end of the second RSV transmission season.
  - Life-threatening SAEs occurring from Day 1 to the end of the second RSV transmission season.
  - Related SAEs occurring from Day 1 to the end of the second RSV transmission season.
  - SAEs occurring within 30 days of vaccination.
  - LRTI associated with RSV infection (AE of special interest) occurring from Day 1 to the end of the second RSV transmission season.
  - Spontaneous or excessive bleeding (AE of special interest) occurring within 30 days after each vaccination.
- The IDMC will receive the following safety data monthly:
  - Summary reports of solicited and unsolicited AEs. (during the period of vaccination).
  - Cumulative reports of the incidence of RSV RTI, RSV-LRTI, severe RSV-LRTI, very severe RSV-LRTI and RSV-RTI leading to hospitalization based on [Table 6](#) by using local test results until the quantitative PCR results are available.
  - Cumulative tables of incidence of all SAEs.

Additionally, an analysis on occurrence of the progression from infection to very severe RSV-LRTI from first vaccination (Day 1) up to the end of the first RSV transmission season will be conducted on all subjects who have completed Visit 7 (end of the first RSV transmission season) by independent Data Analysis Center if there are minimum of 5 infections among subjects with a negative RSV exposure status (at screening which will be assessed by in-stream serological testing of baseline samples) in each randomized group.

In addition, the IDMC will receive from GSK Biologics:

- New information that may adversely affect the safety of the subjects or the conduct of the study.
- All subsequent protocol amendments, informed consent changes or revisions or other documents originally submitted for review.
- All subsequent protocol administrative changes (for information).

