**10.2.1. Subject withdrawal from the study**

From an analysis perspective, a ‘withdrawal’ from the study refers to any subject who did not come back for the concluding visit foreseen in the protocol.

All data collected until the date of withdrawal/last contact of the subject will be used for the analysis.

A subject is considered a ‘withdrawal’ from the study when no study procedure has occurred, no follow-up has been performed and no further information has been collected for this subject from the date of withdrawal/last contact.

Investigators will make an attempt (e.g., three telephone calls and a certified letter to the last known address) to contact those subjects who do not return for scheduled visits or follow-up.

Information relative to the withdrawal will be documented in the eCRF. The investigator will document whether the decision to withdraw a subject from the study was made by the subject's parent(s)/LAR(s), or by the investigator, as well as which of the following possible reasons was responsible for withdrawal:

- Serious adverse event.
- Unsolicited non-serious adverse event.
- Solicited adverse event
- Protocol violation (specify).
- Consent withdrawal, not due to an adverse event\*.
- Moved from the study area.
- Lost to follow-up.
- Other (specify).

\*In case a subject is withdrawn from the study because he/she/the subject's parent(s)/LAR(s) has withdrawn consent, the investigator will document the reason for withdrawal of consent, if specified by the subject/subject's parent(s)/LAR(s), in the eCRF.

Subjects who are withdrawn from the study because of SAEs/AEs must be clearly distinguished from subjects who are withdrawn for other reasons. Investigators will follow subjects who are withdrawn from the study as result of a SAE/AE until resolution of the event (see Section 9.5.1.1).

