## 11.4. Determination of sample size

The sample size determination is based on the minimum number of subjects needed to allow detection of a serious ERD signal having a magnitude similar to that of the historic FI-RSV vaccine trials [Kim, 1969]. A total of 150 infants will be enrolled and randomized with 1:1:1 ratio to receive either 1 dose of the  $1.5 \times 10^{10}$  vp/dose ChAd-155 RSV vaccine [the 1D RSV + comparator group], 2 doses of the  $5 \times 10^{10}$  vp/dose ChAd-155 RSV vaccine [the 2D RSV + comparator group], or no ChAd-155 RSV vaccine [the comparator/Placebo control alone group].

[figure not shown]
An effect of vaccination on ERD will be monitored very closely. It is anticipated that at least 50% of subjects [Dunn, 2013] will have a negative RSV exposure status (at screening which will be assessed by in-stream serological testing of baseline samples). While the rate of RSV infection could be highly variable by season, a conservative rate of infection of 20% in the first season is assumed [Kutsaya, 2016]. Therefore, with 50 infants in each RSV vaccine group, it is anticipated to observe at least 5 infected infants with a negative RSV exposure status (at screening based on in-stream baseline serological testing) in each RSV vaccine group [ $50 \times 0.5 \times 0.2 = 5$ ].

With a one-sided type I error of 0.05, and the assumption of a 10% rate of infection progressing to very severe RSV-LRTI (which is a conservative assumption based on the rate in the natural history of disease), 5 infections can provide at least 90% statistical power to demonstrate the progression rate from infection to very severe RSV-LRTI is less than 80%. That is less extreme than that observed in the historic FI-RSV vaccine trial where 80% of RSV RTI cases progressed to hospitalization [Kim, 1969]. During the course of the study, since the actual negative RSV exposure status (at screening based on in-stream baseline serological testing) and infection rates may be lower than 50% and 20%, respectively, the sample size **may** be adjusted as needed through additional recruitment in order to achieve **a sufficient number of** RSV infected infants with a negative RSV exposure status (at screening based on in-stream baseline serological testing) in each RSV vaccine group (**Amended 1 August 2019**).

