### 11.12.2. Statistical considerations for interim analyses

No interim analyses are planned.

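### The additional IDMC analysis of progression to very severe RSV-LRTI is worded to count only Visit 7 completers and to run only if all three groups reach 5 infections, so it can lose the worst cases and, at the planning rates, would usually not be run

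*Protocol*

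**What the plan says.** Section 9.10.3 of the protocol lists what the IDMC receives within 48 hours and monthly, and then adds one further analysis, of progression from RSV infection to very severe RSV-LRTI between first vaccination and the end of the first season. Its population and timing are given as "will be conducted on all subjects who have completed Visit 7 (end of the first RSV transmission season) by independent Data Analysis Center". Its trigger is "if there are minimum of 5 infections among subjects with a negative RSV exposure status", to be met "in each randomized group". There are three such groups: one-dose RSV, two-dose RSV, and comparator/placebo.

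Three other places bear on this:

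- Section 10.2.1, on withdrawals: "All data collected until the date of withdrawal/last contact of the subject will be used for the analysis".
- Section 11.10 analyses RTI and LRTI primarily on the Exposed Set of infants with a negative RSV exposure status. It sets no completion requirement and no minimum count.
- Sections 11.4 and 11.11 give the decision rules. With 5 infections, at most 1 very severe case excludes an 80% progression rate, and 3 or more indicate a rate above the 10% of natural history. Both rules compare one vaccine group with a fixed value.

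**The concern.** Two features of the sentence in section 9.10.3 work against its purpose.

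The first is the population. Completing Visit 7 is a post-randomization event that depends on the outcome being measured. An infant who dies of RSV-LRTI cannot complete the visit, and a family may withdraw after a severe episode; section 10.2.1 lists a serious adverse event among the reasons for withdrawal. Dropping these infants moves the observed progression rate down. Section 1.1.3 of the protocol records two deaths in the historic formalin-inactivated vaccine trial, so the excluded outcome is the one of greatest interest.

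The second is the trigger. Because all three groups must reach 5 infections, a low count in the control group stops the analysis for a vaccine group that has enough infections, although the rules in 11.4 and 11.11 use no control data. Section 11.4 plans for an expected count of exactly 5 per vaccine group, so the threshold sits at the planning mean.

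What is at stake is the only formal progression estimate that the protocol assigns to the IDMC, in a study meant to support moving to younger infants.

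**Working it through.** **Inputs (section 11.4 unless stated).** "A total of 150 infants will be enrolled and randomized with 1:1:1 ratio", so 50 per group. RSV-negative at screening: "It is anticipated that at least 50% of subjects" (50% used). Infection: "a conservative rate of infection of 20% in the first season is assumed". Reference progression rates: 10% (natural history) and 80% (historic trial). One-sided alpha 0.05. Trigger: 5 infections in each of three groups (9.10.3).

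**Reproducing the plan's own figures.** Expected infections per vaccine group: 50 × 0.5 × 0.2 = 5. Rule of at most 1 very severe in 5:

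- Power at a true 10%: 0.9^5 + 5 × 0.1 × 0.9^4 = 0.590 + 0.328 = 0.919. The stated figure of at least 90% is confirmed.
- Error at a true 80%: 0.2^5 + 5 × 0.8 × 0.2^4 = 0.0067.
- Harm rule, 3 or more of 5 at a true 10%: 0.0081 + 0.00045 + 0.00001 = 0.0086.

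**Effect of the completer restriction.** Take 6 infections with 3 very severe, and let one of the three die or be withdrawn before Visit 7.

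- All infected infants: P(X ≥ 3 | n = 6, p = 0.1) = 0.01458 + 0.00122 + 0.00005 + 0.000001 = 0.016. This is a signal at one-sided 0.05.
- Completers only: P(X ≥ 2 | n = 5, p = 0.1) = 1 − 0.919 = 0.081. The signal is gone.

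Section 11.4 states the harm rule for 5 infections only; its application to 6 uses the same exact test. The example meets the 5-infection trigger whether or not the lost case is counted towards it.

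**Chance that the trigger is met.** The number of RSV-negative infected infants in a group of 50 is Binomial(50, 0.5 × 0.2 = 0.10).

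- One group: P(X ≥ 5) = 0.569.
- Both vaccine groups: 0.569² = 0.324.
- All three groups: 0.569³ = 0.184.

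With exactly 25 RSV-negative infants per group, Binomial(25, 0.2), the three-group figure is 0.194.

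**Sensitivity of the three-group chance to the rates.**

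| RSV-negative | Infected | Expected per group | All three groups |
|---|---|---|---|
| 50% | 15% | 3.75 | 3.3% |
| 50% | 20% | 5.0 | 18% |
| 60% | 20% | 6.0 | 39% |
| 50% | 25% | 6.25 | 45% |
| 70% | 20% | 7.0 | 61% |
| 50% | 30% | 7.5 | 70% |

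These figures treat the groups as independent. A season effect shared by all groups, assumed here as a standard deviation of 5 to 10 percentage points in the infection rate, raises 18% to between 23% and 28%. At the planning rates, a 50% chance of meeting the trigger needs about 66 infants per group.

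**The case against.** Several points on the other side stand.

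- A reader might infer that the trial's main analysis of enhanced disease is biased or withheld. It is not. Sections 11.10 and 11.11 carry the endpoint analysis, on the Exposed Set of RSV-negative infants and with no trigger, and 11.12.1 schedules it when data to Visit 7 are available.
- A reader might infer that deaths are hidden from the IDMC. They are not. It works unblinded, receives fatal and life-threatening SAEs and RSV-LRTI cases within 48 hours, and receives monthly cumulative tables that include very severe RSV-LRTI.
- Section 11.12.2 states "No interim analyses are planned". That does not deny this analysis exists: 11.12.1 provides for safety analyses by an independent data analysis center for the IDMC.
- It is tempting to say that one lost case readily reverses the 80% conclusion, since 2/5 has an exact one-sided upper limit of 81.1% and 1/4 has 75.1%. That needs an analysis with 4 completer infections. If only completers count towards the trigger, it would not run; the first reversal is then 4/8 (80.7%) to 3/7 (77.5%). Equally, the 2% chance of meeting the trigger at 30% attrition holds only if completers alone count, and section 11.4 uses 30% attrition only for the width of an AE interval.
- The planning rates are worded as a minimum and as conservative, and extra recruitment is allowed. That recruitment is optional, has no fixed number, and is aimed at the vaccine groups, not at control.
- A minimum in control could be defended, because section 1.2.4.1 names comparison with controls as one way to detect enhanced disease. That supports showing control data; it does not support withholding a vaccine group's one-sample result.
- The Amendment 3 rationale suggests that Visit 7 may be meant as a data cut. The operative sentence nevertheless names a population of completers, so it needs correcting on either reading.

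**Conclusion.** The point holds for this one additional IDMC analysis. Followed literally, section 9.10.3 selects infants on an event that depends on the outcome, contrary to 10.2.1 and 11.10, and the loss of a single case can remove a harm signal (P = 0.016 to P = 0.081 in the example). Its three-group trigger would be met about 18% of the time at 50% RSV-negative, 20% infected and 50 per group, against 57% for one vaccine group. The statement that it would usually not be run therefore rests on those planning rates and on no extra recruitment; at 70%/20% or 50%/30% it would more likely than not run (61% and 70%). The documents do not support extending the criticism to the end-of-season analysis or to the IDMC's other reports.

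**What to change.** Reword the paragraph in section 9.10.3 so that the analysis covers all vaccinated RSV-negative infants with RSV infection, uses data to Visit 7 or last contact, and counts deaths and withdrawals. Report each RSV vaccine group with its exact one-sided limit at the end of the first season whatever the number of infections, with control shown descriptively. If a minimum count is kept, apply it to each RSV vaccine group separately. Naming the analysis in 11.12.1 among those prepared for the IDMC would make its status clear.

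The cost is a one-paragraph amendment with matching IDMC charter wording, and no new data. The downside is that the IDMC may see estimates based on few infections; the exact limits will show how little these establish.
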